#### Assessments:

All subjects will undergo a brief set of assessments during the third supervised therapy session then again every 3 supervised sessions until the end of therapy. These assessments will record adverse events (which includes study-related adverse events, serious adverse events, and interval medical history), ascertain subject compliance with the unsupervised therapy sessions, document any new medications, and document the amount of any therapy (OT, PT, SLT) that the subject received outside of study procedures. At the end of supervised sessions 6 and 12, the subject will be briefly asked about any new interval medical history events. In addition, at the end of supervised session 3 and supervised session 18, the PACES, OPS scale, and Patient Satisfaction Questionnaire will each be completed. These brief assessments will be performed by the subject's Treatment Therapist.

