**5.3.3.1 Additional details for subjects randomized to in-clinic therapy:**

The 18 supervised therapy sessions will take place at the central study site. A Treatment Therapist will provide continuous supervision throughout each of these 80 minute treatment sessions. A revised treatment plan will be generated and implemented after 6 supervised sessions and again after 12 supervised sessions of therapy.

The 18 unsupervised therapy sessions will take place in the patient's home, and will be guided by an individualized booklet generated and printed by the Treatment Therapist and distributed to the subject during the first in-clinic therapy visit. The content of the unsupervised therapy sessions will be matched to the same exercise and training components provided during the subject's in-clinic supervised therapy sessions. After 6 supervised sessions and again after 12 supervised sessions of therapy, the booklet guiding the unsupervised therapy session will be returned to the therapist, at which time a new booklet will be provided to the subject, containing a revised therapy plan. At the start of each of the 18 unsupervised sessions, all subjects will receive 5 minutes of stroke education. As with the other content of the unsupervised sessions, stroke education will be delivered by booklets provided by the Treatment Therapist during a supervised therapy session. Using a large Helvetica font, a multiple-choice question is presented, the patient marks his/her answer, then the patient is provided with the correct answer along with a brief explanation. This is repeated four times, for a total of five questions at each unsupervised session.

If there are any unsupervised therapy sessions completed after a subject's final supervised therapy session, the Treatment Therapist will call the patient at home and collect data on compliance for any such sessions.

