**Compliance and motivation.**

- Compliance with therapy, defined as the percentage of the 36 therapy sessions for which the subject completed assigned activities for at least 40 minutes

Compliance with rehabilitation therapy will be examined across all 36 sessions. For supervised sessions, a subject will be considered compliant if at least 40 min of assigned

therapy has been completed, determined from the therapist notes for subjects in the in-clinic group and from telerehabilitation system usage data for subjects in the telerehabilitation group. For unsupervised sessions, a subject will be considered compliant if at least 40 min of assigned therapy has been completed based on self-report for the in-clinic group and by telerehabilitation system usage data for subjects in the telerehabilitation group. To determine whether compliance with therapy differs according to treatment group, ANCOVA modeling will be used to examine compliance across the 36 sessions as a function of treatment group, controlling for days from stroke onset to randomization, age, and enrollment site. Secondary analysis will examine compliance with only the supervised therapy sessions, as well as compliance with only the unsupervised sessions.

**Motivation** (assessed along two independent dimensions):

- Activity-inherent motivation, defined as the change in score on the Physical Activity Enjoyment (PACES) Scale from baseline to end of the first week of therapy
- Consequence-related motivation, defined as the score on the Optimization in Primary and Secondary Control (OPS) Scale at the Baseline Visit

Activity-inherent motivation reflects how much a subject likes or dislikes an activity itself, independent of his or her commitment to the treatment goals. To measure this, the PACES Scale will be scored three times (at the Baseline Visit, after 3 supervised sessions, and after 18 supervised sessions). Activity-inherent motivation will be defined as the change in PACES score. Primary analysis will examine the change from baseline to end of week 1, while secondary analysis will examine change from baseline to end of week 6. To determine whether activity-inherent motivation is different for in-clinic vs. telerehabilitation therapy, ANCOVA modeling will examine differential change in PACES score between the two treatment groups, controlling for days from stroke onset to randomization, PACES score at the Baseline Visit, age, and enrollment site.

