Consequence-related motivation reflects a subject's level of commitment to treatment goals. To measure this, the OPS Scale will be scored three times (at the Baseline Visit, after 3 supervised sessions, and after 18 supervised sessions). We hypothesize that across both treatment groups, the baseline level of consequence-related motivation (OPS score at the Baseline Visit) will predict compliance with rehabilitation therapy. Furthermore, we hypothesize that when consequence-related motivation is high compliance will be high for both treatment groups, however when consequence-related motivation is low compliance may be lower overall but will vary with the level of activity-inherent motivation. ANCOVA modeling will be used to determine if consequence-related motivation is a significant predictor of compliance with therapy (as defined above, across all 36 sessions), controlling for days from stroke onset to randomization, age, and enrollment site. Primary analysis will define consequence-related motivation using the OPS subscale that measures selective primary and selective secondary control striving (also referred to as goal engagement). Secondary analyses will define consequence-related motivation using the entire OPS score, and will also examine the effect of treatment group. An additional analysis will examine add the interaction term OPS x PACES to determine whether compliance varies with consequence-related motivation in a manner that depends on level of activity-inherent motivation; PACES and OPS scores will be centered and then combined in the interaction term.

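### Half of the 36-session compliance outcome is self-reported in-clinic but system-logged in telerehabilitation, and the plan has no sensitivity analysis for misreporting in this secondary Aim 3 comparison

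*Combined protocol and SAP*

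**What the plan says.** Section 1.3.1 hypothesizes that compliance under telerehabilitation will match or exceed in-clinic compliance. Compliance is the percentage of the 36 sessions in which at least 40 minutes of assigned activity was completed. Section 8.5 (Compliance and motivation) gives the data sources:

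- **Supervised sessions (18):** "determined from the therapist notes for subjects in the in-clinic group and from telerehabilitation system usage data" for the telerehabilitation group.
- **Unsupervised sessions (18):** "based on self-report for the in-clinic group and by telerehabilitation system usage data for subjects in the telerehabilitation group".

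The main test is stated as "ANCOVA modeling will be used to examine compliance across the 36 sessions as a function of treatment group", adjusted for days from stroke onset to randomization, age and site. The plan adds: "Secondary analysis will examine compliance with only the supervised therapy sessions", and likewise the unsupervised sessions alone.

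On collection, section 5.3.3 (Assessments) has all subjects assessed "during the third supervised therapy session then again every 3 supervised sessions until the end of therapy", partly to "ascertain subject compliance with the unsupervised therapy sessions". Section 5.3.3.1 says that after 6 and 12 supervised sessions "the booklet guiding the unsupervised therapy session will be returned to the therapist", and that the therapist telephones about any unsupervised session done after the last supervised one. Neither section says that the booklet is used to verify compliance. The only analysis that the plan calls a sensitivity analysis (section 8.1) concerns efficacy in the Per-Protocol Population.

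**The concern.** Randomization does not protect this comparison, because the way unsupervised compliance is measured is assigned together with the treatment. Any systematic gap between what in-clinic subjects report and what a log would have recorded goes straight into the estimated arm difference. Days post-stroke, age and site carry no information about that gap.

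Run as written, the 36-session ANCOVA could show a difference that is only measurement, or hide a real one. What is at stake is the between-arm conclusion under section 1.3.1. In-clinic over-reporting would work against the telerehabilitation hypothesis, and under-reporting would favor it.

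The pilot in section 3 gives a reason to look: subjects' recall of the previous day's scores and usage was not significantly related to the actual values.

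**Working it through.** **Plan's own figures.** The documents give no SD, margin, power or sample size for compliance. The only sample size is for the Fugl-Meyer endpoint (section 8.3): margin 2.05, SD 4.0, 80% power, 62 per arm. A noncentral-t calculation needs 61 per arm, and power at 62 is 81%. Dropout inflation is 124/0.8 = 155. These figures reproduce, and the group sizes are borrowed below.

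**Step 1: shift in the outcome (documents only).** For each subject, 36-session compliance = (18/36) × supervised % + (18/36) × unsupervised %. Let *r* be net misreporting of in-clinic unsupervised compliance in percentage points, positive for over-reporting, with the log taken as accurate. Then

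observed difference (telerehabilitation − in-clinic) = true difference − 0.5 × *r*.

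With *r* = 10 (1.8 of 18 sessions), the shift is 5 points. The unsupervised-only analysis takes the full 10.

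**Step 2: ceiling.** Reported compliance cannot exceed 100%, so *r* ≤ 100 − true unsupervised compliance.

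- A 5-point over-reporting shift needs *r* = 10, hence true in-clinic unsupervised compliance of 90% or lower.
- At the pilot's level, 329/336 = 97.9%, *r* ≤ 2.1 and the shift is at most 2.1/2 ≈ 1 point. The pilot counted days engaged in telerehabilitation, not 40-minute sessions from a booklet, so this is only a reference value.
- Under-reporting is not limited in this way.

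**Step 3: effect on the test (illustration only; the SDs are assumed).** SE = SD × √(2/62). The chance of a false significant difference in the direction of a 5-point shift is 1 − Φ(1.96 − 5/SE), against a nominal 2.5%. Masking sets a real 10-point difference against an opposing 5-point shift.

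| Assumed SD | SE | Critical difference (1.96 × SE) | False difference from 5-point shift | Power for real 10 points, no shift | Same, with opposing 5-point shift |
|---|---|---|---|---|---|
| 15 | 2.69 | 5.28 | 46% | 96% | 46% |
| 20 | 3.59 | 7.04 | 29% | 80% | 29% |
| 25 | 4.49 | 8.80 | 20% | 61% | 20% |

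If 155 subjects are analyzed, the false-difference figures are 55%, 34% and 24%.

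A variable bounded at 0–100% has SD ≤ √(m(100 − m)) at mean m. These SDs are therefore possible only if mean compliance is at most 97.7%, 95.8% and 93.3% respectively. At 97.9% the SD cannot exceed about 14.3, so the table does not describe a trial with pilot-level compliance.

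**Step 4: motivation model.** The primary model relating the OPS score to compliance uses the same outcome and leaves treatment group to later: "Secondary analyses will define consequence-related motivation using the entire OPS score, and will also examine the effect of treatment group". With a 5-point shift (b), an assumed 0.2 SD difference in OPS between arms (d) and an assumed compliance SD of 20, the slope bias is b·d/4/(1 + d²/4) = 0.25 points per OPS SD. The slope SE is 20/√124 = 1.80, so the rejection rate is 5.2% against 5%. This is negligible.

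**The case against.** The strongest reply is that the plan already provides much of the protection. It states its data sources openly, and the supervised-only analysis contains no self-report. Read with the unsupervised-only analysis, it would show whether a 36-session difference arises only in the self-reported half. This stands as a partial safeguard. It does not close the gap: supervised attendance is a narrower question, that analysis still compares therapist notes with system logs, and nothing ties either result to the conclusion under section 1.3.1.

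Second, collection is roughly weekly, and in-clinic subjects mark education answers in a booklet at each unsupervised session. That is a trace of a session being started, not of 40 minutes completed. Section 5.3.3 might also mean that telerehabilitation subjects are asked about compliance, which would allow a check of self-report against the log in that arm. The text does not give the method, and section 8.5 uses no such check.

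Third, compliance may be too high for over-reporting to matter. Near the pilot's level that is right. The pilot does not show what booklet users at home would do, and the ceiling does not restrict under-reporting.

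Some stronger readings are tempting but not supported:

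- **That the pilot shows self-report here to be invalid.** It had 12 subjects, all on telerehabilitation, recalling scores and usage. They were not reported to have been asked to confirm a 40-minute session.
- **That the bias has a known direction.** The documents give none.
- **That the primary result is affected.** The Fugl-Meyer intent-to-treat analysis does not use compliance. The Per-Protocol set in section 8.1 counts supervised sessions only, although it shares the notes-versus-logs difference.

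**Conclusion.** The concern holds for the secondary compliance comparison and no further. For 18 of 36 sessions, data source coincides with arm, the covariates cannot remove a reporting difference, and no misreporting analysis is planned. The one figure that rests on the documents alone is the conversion: 10 points of net misreporting on unsupervised sessions gives 5 points on the 36-session scale. For over-reporting this is bounded by the ceiling, at about 1 point if true in-clinic unsupervised compliance equals the pilot's 97.9%. The false-difference and masking percentages rest on assumed SDs and an assumed misreport rate and are not predictions.

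A reader might also infer that a non-significant ANCOVA would support comparability once misreporting is addressed. It would not: neither section 1.3.1 nor section 8.5 states a compliance margin, and the ANCOVA tests only for a difference. Nor do the documents offer a basis for a largest plausible misreport rate, so a decision rule built on one would be arbitrary.

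The change is worth making because it is cheap and should be fixed before the data are seen. The effect on the motivation model is negligible.

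**What to change.** In section 8.5:

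1. Keep the 36-session ANCOVA and prespecify a sensitivity analysis. Shift each in-clinic subject's unsupervised compliance by an assumed net misreport rate, in 5-percentage-point steps from 0 in both directions and bounded at 0–100%. Recompute the 36-session percentage and refit the ANCOVA. Report the rate, and the mean shift it produces, at which the between-arm difference gains or loses statistical significance.
2. Report the supervised-only result beside the 36-session result, and label 36-session and unsupervised compliance as measured differently by arm. Do not attribute a 36-session difference to treatment on that test alone if it appears only in the unsupervised half or reverses at a small misreport rate. State that a non-significant ANCOVA will not be read as comparability.
3. Optional: include treatment group in the primary OPS–compliance model.

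The cost is some wording, one table and, if taken up, one model term. No new data are needed, and the 36-session outcome and main analysis stay as they are. The downside is a more cautious secondary conclusion.

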### 1.2 Specific Aim 2. Secondary Outcomes--Stroke Education and Prevention:

Many patients with stroke know little about the causes of their condition and consequently have poor control of stroke-related risk factors. Improving patient knowledge about stroke can therefore help to prevent stroke recurrence and to optimize patient outcomes. While all certified stroke centers include patient education as a priority during the acute stroke admission, patients and their families may not be in the best position to benefit from such education at this time as compared to once they have returned to their home. Aim 2 will compare two different approaches to patient education in their impact on stroke knowledge, hypothesizing that both are effective, and are effective to an equal extent. As an extension of this issue, the degree of gains in stroke knowledge is hypothesized to be related to the extent to which patients implement appropriate lifestyle changes.

**1.2.1** Subjects, having received targeted educational material for 6 weeks, will significantly increase knowledge related to stroke prevention and stroke risk factor control, measured as the change in percentage of questions answered correctly on the Stroke Education Exam from Screening Visit to Post-Therapy Visit.

**1.2.2** The change in percentage of questions answered correctly on the Stroke Education Exam from Screening Visit to Post-Therapy Visit among subjects using the telerehabilitation system will be comparable to the change in percentage of questions answered correctly on the Stroke Education Exam among subjects using a traditional paper booklet-based method.

**B.1.3** Increased stroke knowledge will be positively correlated with improvement in weight and blood pressure control.

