### 1.3 Specific Aim 3. Patient Compliance with and Motivation for Therapy:

A major issue in rehabilitation therapy is patient compliance. Compliance and its variance across patients will be examined by measuring two dimensions of motivation. Aim 3 hypothesizes that compliance and activity-inherent motivation will be comparable across the two study treatment groups, and that compliance will vary with consequence-related motivation.

**1.3.1** Compliance with therapy, defined as the percentage of the 36 therapy sessions for which the subject completed assigned activities for at least 40 minutes, will be comparable or better with telerehabilitation as compared to compliance with in-clinic therapy.

**1.3.2** Activity-inherent motivation, which reflects how much a patient enjoys a therapy and defined as the change in score on the Physical Activity Enjoyment (PACES) Scale

from the Baseline Visit to end of the first week of therapy, will be at least as high (and in many patients higher) with telerehabilitation as compared to in-clinic therapy.

**1.33** Level of consequence-related motivation, which reflects the patient's degree of dedication to treatment goals and defined as the score on the Optimization in Primary and Secondary Control (OPS) Scale at the Baseline Visit, will emerge as a significant predictor of compliance in both groups, even after controlling for key variables. When consequence-related motivation is high, compliance will be high, for both treatment groups. When consequence-related motivation is low, compliance may be lower but will vary with the level of activity-inherent motivation.

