## 8. STATISTICAL CONSIDERATIONS, DATA ANALYSIS AND DATA MONITORING

In the study, populations used for testing comparable efficacy, the non-inferiority margin proposed for determining comparable efficacy, the statistical procedures used for summarizing and testing the primary and secondary comparable efficacy endpoints, and sample size justification for the proposed study. All analyses are two-tailed and use  $\alpha=0.05$ .

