**8.5 Secondary outcome measures:****Stroke education**

- Gains in stroke knowledge from Screening Visit to Post-Therapy Visit, measured as the change in percentage of questions answered correctly on the Stroke Education Exam

In order to determine whether targeted educational material significantly increases subject knowledge related to stroke, the Stroke Knowledge Exam will be administered twice, once at the Screening Visit then again at the Post-Therapy Visit. A repeated measures ANOVA will be performed to determine if the percentage of Stroke Knowledge Exam answered correctly increases significantly from the Screening Visit to the Post Therapy Visit, controlling for days from stroke onset to randomization, initial Stroke Knowledge Exam score (at the Screening Visit), age, and enrollment site. To determine if gains in stroke knowledge vary according to the method by which stroke education is delivered, analysis will be repeated adding a time X group interaction term. Weight and blood pressure will be measured during the Screening Visit as well as during the Post Therapy Visit. In order to determine whether gains in stroke knowledge are associated with improvements in stroke risk factor control, the relationship between gains in stroke knowledge (the change in percentage of questions answered correctly on the Stroke Education Exam from the Screening Visit to the Post Therapy Visit) and improvement in weight and blood pressure control (change in weight, change in systolic blood pressure, and change in diastolic blood pressure) will be examined, controlling for days from stroke onset to randomization, Stroke Knowledge Exam score at Screening Visit, age, and enrollment site, and using a Bonferroni-adjusted alpha = 0.017; again, analyses will be repeated by adding a time X group interaction term.

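### The aims for stroke knowledge, compliance and therapy enjoyment (PACES) state comparability or non-inferiority, but Section 8.5 plans only two-tailed difference tests, with no limit or confidence-interval rule

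*Combined protocol and SAP*

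**What the plan says.** The hypotheses are in Sections 1.2 and 1.3.

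- **Knowledge.** The introduction to Aim 2 compares two education methods, "hypothesizing that both are effective, and are effective to an equal extent". Sub-aim 1.2.2 is worded more loosely: the gain with telerehabilitation "will be comparable to the change in percentage of questions answered correctly on the Stroke Education Exam among subjects" using the paper booklet.
- **Compliance.** Aim 3 opens by saying that "compliance and activity-inherent motivation will be comparable across the two study treatment groups". Sub-aim 1.3.1 then says that compliance "will be comparable or better with telerehabilitation as compared to compliance with in-clinic therapy".
- **Enjoyment (change in PACES).** Sub-aim 1.3.2 says that it "will be at least as high (and in many patients higher) with telerehabilitation as compared to in-clinic therapy".

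The tests are in Section 8.5. For knowledge, a time-by-group term is added to a repeated measures ANOVA: "To determine if gains in stroke knowledge vary according to the method by which stroke education is delivered". For compliance: "To determine whether compliance with therapy differs according to treatment group, ANCOVA modeling will be used to examine compliance across the 36 sessions". For PACES, an ANCOVA asks whether motivation is different in the two arms. Section 8 sets the error rate for all of them: "All analyses are two-tailed and use" alpha 0.05.

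Section 8.5 gives no limit, no confidence-interval rule and no reading of a non-significant result for these three endpoints. The Fugl-Meyer (FM) endpoint has both a margin of 2.05 points and a rule that the lower 95% bound must exceed -2.05 (Section 8.3). Section 8.4 carries the primary method over to Box & Blocks and SIS-Hand only.

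**The concern.** A difference test asks whether the arms can be told apart. The aims ask whether telerehabilitation is close enough to, or not worse than, in-clinic therapy. These are separate questions, and the plan applies the right logic to FM but not here.

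If the arms turn out similar, which is what the aims predict, the planned tests will mostly be non-significant and the aims will remain undecided. A small but significant deficit would count against an aim even if it had no practical importance. The risk lies in reporting: with no rule written down, a p-value above 0.05 could be offered as evidence that the arms are comparable.

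**Working it through.** **1. The plan's own figure.** Section 8.3 gives a margin of 2.05, SD 4.0, 80% power and 62 per arm. The normal formula n = 2[SD(1.96 + 0.84)/margin]² = 2[4.0 × 2.80/2.05]² gives 59.8, so 60 per arm. The noncentral-t version gives 61, and power at 62 is 80.8%. The stated size is therefore sound for FM, and 124/(1 - 0.20) = 155 is exact. No size, power, SD or limit is given for knowledge, compliance or PACES, so the rest is in SD units.

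**2. Inputs.** 62 per arm (target with 30-day data), and 77 per arm (155 enrolled, no loss before these earlier assessments). Two-sided 0.05. SD means residual SD. The limits of 0.4, 0.5 and 0.6 SD are illustrative assumptions.

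**3. Precision.** SE of the group difference = √(2/n) SD.
- n = 62: SE 0.180 SD, 95% half-width 1.980 × 0.180 = 0.356 SD.
- n = 77: SE 0.161 SD, 95% half-width 1.976 × 0.161 = 0.318 SD.

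**4. How often a true deficit d gives a non-significant result.** Noncentral t, df = 2n - 2, noncentrality d/SE.

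| True deficit | 62 per arm | 77 per arm | 95% lower-bound rule, limit = d |
|---|---|---|---|
| 0.4 SD | 40.1% | 30.6% | 2.5% |
| 0.5 SD | 21.1% | 13.1% | 2.5% |
| 0.6 SD | 8.8% | 4.1% | 2.5% |

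The last column is 2.5% by construction: with the true deficit at the limit, the lower bound of a 95% interval clears it in one case in 40. Normal theory is approximate for compliance, which is a bounded percentage.

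**5. Smallest limit with 80% power when the true difference is zero.**

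| Rule | 62 per arm | 77 per arm |
|---|---|---|
| Lower bound, 95% CI | 0.51 SD | 0.45 SD |
| Both bounds, 95% CI | 0.59 SD | 0.53 SD |
| Both bounds, 90% CI | 0.53 SD | 0.47 SD |

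**6. Why an SD-based limit does not suit compliance.** One of 36 sessions is 100/36 = 2.8 points. If the SD were 5 points, 0.5 SD would be 2.5 points, under one session. If it were 20 points, 0.5 SD would be 10 points, or 3.6 sessions. Both SDs are assumptions.

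**7. What the knowledge model estimates.** There are two visits, and Section 8.5 lists covariates without any covariate-by-time terms. A covariate entered as a main effect shifts both visits equally and cancels from the within-subject change. With complete data the time-by-group term is therefore (mean change, telerehabilitation) - (mean change, in-clinic), unadjusted. In one simulated data set the term and the raw difference in change were both -4.64, while an ANCOVA of change on group and baseline gave -2.93. The values only show that the two estimates differ. Under randomisation neither is biased, but the ANCOVA allows for chance baseline imbalance.

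**8. Own-baseline covariates in Section 8.4.** The primary model adjusts for Baseline FM. Let r be the correlation between an endpoint's baseline and follow-up, and q its correlation with FM. Put r' = (r - q²)/(1 - q²). Adding the endpoint's own baseline then cuts residual variance by (1 - r')/2. For assumed r of 0.7 to 0.9 and q of 0.3 to 0.7, the cut is 5.5% to 29.4%, or 2.8% to 16.0% of the SE.

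**The case against.** The strongest reply is that the plan never says a non-significant result will be taken as comparability. That is correct. A reader might infer that it will, but no section says so. The percentages in step 4 describe a misreading that the plan leaves open, not one it commits to. The mismatch between hypothesis and test remains.

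A reader might also infer that no result could ever support 1.2.2, since significance would contradict equality and non-significance would not prove it. This holds only on a two-sided reading. The equality wording is in the introduction to Aim 2. Sub-aim 1.2.2 says only comparable, and Section 8.3 uses comparable efficacy for a one-sided lower-bound rule. Read one-sidedly, 1.2.2 would be supported by a significant advantage for telerehabilitation. The text does not settle which reading is meant. Aim 3 is clearer: its opening is a summary, which 1.3.1 and 1.3.2 then make one-sided.

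Nor do the documents support the inference that Section 8.4 applies -2.05 to Box & Blocks or SIS-Hand. Section 8.3 ties that margin to FM change, so a note to this effect would be clarification only.

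It is fair to add that the limits used here are illustrative and the endpoints are secondary. Both points stand. The first does not remove the mismatch, which exists at any limit. The second bounds its importance.

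**Conclusion.** The point holds as a mismatch between three secondary hypotheses and their planned tests. A non-significant result in Section 8.5 cannot support 1.2.2, 1.3.1 or 1.3.2. A significant advantage for telerehabilitation would support 1.3.1 and 1.3.2, and 1.2.2 on a one-sided reading.

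If non-significance were nevertheless reported as comparability, a true deficit of 0.4, 0.5 or 0.6 SD would pass 40%, 21% or 9% of the time at 62 per arm (31%, 13% or 4% at 77), against 2.5% under the interval rule. These sizes rest on assumed limits and normal theory with equal SDs. The primary FM analysis, its margin and N = 124 are not affected. The change should be made, but the trial's main conclusion does not depend on it.

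**What to change.** In Section 8.5:

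1. For all three endpoints, report the group difference with its 95% CI, and state that non-significance will not be read as comparability.
2. For knowledge, take the difference from an ANCOVA of change on group, Screening score and the covariates already listed, because the time-by-group term as planned gives the unadjusted difference. Leave the test of 1.2.1 as it is.
3. Claim comparability only if the interval excludes an endpoint-specific limit fixed before data are compared by arm. Use the lower bound for 1.3.1 and 1.3.2. For 1.2.2, state whether one or both bounds apply and at what CI level.
4. Express the compliance limit in percentage points or sessions.
5. Where no limit can be justified, give the estimate and interval and make no comparability claim.

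An interval rule does not cure one further problem: compliance with unsupervised sessions is self-reported in the in-clinic arm and system-logged in the telerehabilitation arm. The report should say so next to any compliance claim.

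A minor improvement in Section 8.4 is to add Screening Box & Blocks and Baseline SIS-Hand as covariates in their own models. Both are already collected, and the size of the gain rests on assumed correlations.

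The cost is SAP text and slightly more analysis work, with no new data or visits. The downside is that some secondary comparability claims become harder to make or are dropped, since 62 per arm gives 80% power only for limits of about 0.5 to 0.6 SD or wider.
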